7. INFORMED CONSENT PROCESS

The informed consent will be conducted by [name] in the SAHP Neuroscience Research Laboratory with a single potential subject at a time. Participants will have the opportunity to ask questions before deciding to participate. Those participants who meet inclusion criteria will be identified by a code on all documents other than their signature on the informed consent. Twenty participants with no pain will be in the normal group. Forty participants with chronic subclinical neck or upper quadrant pain will be randomized (random number table will be used) into two groups: twenty subjects in the control group, and twenty subjects in the intervention group. All participants' records will be stored in a locked cabinet, in a locked office and stored on a secure drive.

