First, participants in the normal group (20 subjects) will first be instructed to complete the VAS for pain, a subjective measure of pain intensity consisting of a 10 centimeter (cm) line with anchor statements on the left (no pain) and extreme pain on the right. Pain scores will be determined by measuring the distance in cm from “no pain” to the participant’s anchor point. In this group the score must be “no pain” or 0 cm. Participants randomly assigned to the control group (20 subjects) will first be instructed to complete the VAS for pain with a score less than 4/10 required. Participants randomly assigned to the intervention group (10 subjects) that will receive daily SMS text message reminders for compliance during intervention will first be instructed to complete the VAS for pain with a score less than 4/10 required. Participants randomly assigned to the intervention group (10 subjects) that will not receive daily SMS text message reminders for compliance during intervention will first be instructed to complete the VAS for pain with a score less than 4/10 required.

Next, all participants in all groups will complete 2 self-report questionnaires beginning with the STAI-form Y which is a definitive clinical measure of state and trait anxiety in adults. Form Y has 20 items for assessing trait anxiety and 20 for state anxiety. All items are rated on a 4-point scale (e.g., from “Almost Never” to “Almost Always”). Higher scores indicate greater anxiety.

Next, all participants in all groups will complete the NDI questionnaire which consist of 10 sections (pain intensity, personal care, lifting, work, headaches, concentration, sleeping, driving, reading and recreation) with questions that are measure in a 6-point scale from 0 (no disability) to 5 (full disability). The numeric responses will be added with a score varying from 0-50 where 0 is considered “no activity limitation” and 50 is considered “complete disability.” Furthermore, 0-4 (no disability), 5-14 (mild disability), 15-24 (moderate disability), 25-34 (severe disability) and greater than 35 (complete disability).

Next, all participants in all groups will be familiarized with the Noraxon myoMotion™ system instrument that utilizes inertial measurement units (IMUs) to

measure angles of motion in joints which will measure cervical spine proprioception utilizing the joint position error (JPE) test.

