Data was analyzed using SPSS version 28.0. Assuming a moderate effect size of 0.3, a power of 0.80, an alpha of 0.05 and 15% dropout rate, the estimated sample size was 40 participants. Data was summarized using frequency (%) for qualitative variables, mean \pm standard deviation (SD) for continuous variables, and median (minimum, maximum) when the distribution was not approximately normal. The normality of the outcome variables was examined using the Shapiro wilk test and boxplots. The frequency distribution of gender between the two study groups was compared using Fisher's exact test. Mean baseline characteristics and outcome variables by study group was examined using independent t-test. Median VAS, NDI, and JPE rotation right were compared between the intervention and control groups using Mann-Whitney U test. For each study group, changes in mean outcome variables (cervical spine AROM, anxiety, neck proprioception, VAS, NDI) over time (post versus pre) were examined using paired t-test or Wilcoxon signed rank test when the distribution is not approximately normal. Changes in outcome variables by group (intervention versus control) overtime (post 2 weeks versus pre) were assessed using 2x2 mixed factorial analysis of variance (ANOVA). If there was a significant interaction between group and time, the changes are significantly different between the two groups. There was a significant difference in mean STAI_T and lateral flexion left between the intervention and control groups at baseline, thus this was controlled for baseline differences using analysis of covariance (ANCOVA). In the intervention group, we examined changes in outcome variables over time (pre versus post 30 minutes versus post 2 weeks) using repeated measures ANOVA or Friedman's test if the data was not approximately normal. If the results were significant, Bonferroni's post hoc comparisons were conducted, or Wilcoxon signed rank test were used to determine what times were significantly different. The level of significance was set at $p \leq 0.05$.

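### ANCOVA appears to have been triggered by a significant baseline test; using it for every randomised outcome costs almost nothing and, unless the pre-post correlation is high, is more precise than the change-score test

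*SAP*

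**What the plan says.** The SAP is a single paragraph in the past tense. Between-group comparisons appear in four places.

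- Baseline: "Mean baseline characteristics and outcome variables by study group was examined using independent t-test".
- Rank tests, with no time point given: "Median VAS, NDI, and JPE rotation right were compared between the intervention and control groups using Mann-Whitney U test".
- Change over time by group: "post 2 weeks versus pre) were assessed using 2x2 mixed factorial analysis of variance (ANOVA", with a significant group-by-time interaction read as a difference in change.
- Baseline adjustment: "There was a significant difference in mean STAI_T and lateral flexion left between the intervention and control groups at baseline, thus this was controlled", by ANCOVA. This is the only mention of ANCOVA in either document.

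Protocol section 11 (Data Analysis) names ANOVA only. Protocol section 7 says that the forty participants with pain "will be randomized (random number table will be used) into two groups", twenty per group. The SAP's planning inputs are: "Assuming a moderate effect size of 0.3, a power of 0.80, an alpha of 0.05 and 15% dropout rate", giving 40 participants. Neither document states a pre-post correlation.

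**The concern.** The comparison is randomised, so baseline differences between the two pain groups arise by chance. A significance test on them says nothing useful about whether to adjust. It also lets the data choose the model outcome by outcome, and it fires only at large gaps.

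Outcomes that do not trip the test fall back on the change score, which in effect fixes the slope on the baseline value at 1. When the pre-post correlation is below 1 and the SDs are equal, that slope is too steep. A chance baseline gap is then over-corrected and the treatment estimate is noisier than it need be. With 40 participants and 15% expected attrition, precision matters.

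The ANCOVA sentence also does not say which models were adjusted, or for what.

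**Working it through.** **Inputs.** From the documents: 20 per arm, 15% dropout (40 x 0.85 = 34, taken as 17 per arm), alpha 0.05 (two-sided here). Assumed: pre-post correlation rho from 0.3 to 0.9, equal pre and post SDs unless stated, and a 0.6 SD effect for illustration.

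**The plan's own figure.** The SAP does not say what its 0.3 measures. If it is Cohen's f for the 2x2 interaction, noncentrality is N x f^2 x 2/(1 - rho). At N = 34 and rho = 0.3 this is 34 x 0.09 x 2/0.7 = 8.74, giving 82% power; N = 32 gives 79%. So 34 are needed, and 34/0.85 = 40. Other inputs also reach 40: f = 0.25 with rho = 0.5 needs 34. But f = 0.3 with rho = 0.5 needs only 24 (29 after dropout), and a standardised mean difference of 0.3 would need 175 per arm. The figure of 40 is attainable but does not pin down rho.

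**Precision.** With n per arm, N = 2n and SD sigma:

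- Var(change) = 2 sigma^2 (1 - rho) x 2/n
- Var(ANCOVA) = sigma^2 (1 - rho^2) x (2/n) x (N - 3)/(N - 4); the last factor is the cost of estimating the slope
- Ratio ANCOVA/change at N = 34: (1 + rho)/2 x 31/30

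**Power, 0.6 SD effect.** Change score: noncentral t, 32 df, noncentrality 0.6/sqrt(2(1 - rho) x 2/17). ANCOVA: noncentral t, 31 df, averaged over the chance baseline gap.

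| rho | Variance ratio | Noncentrality (change) | Power, change | Power, ANCOVA |
|---|---|---|---|---|
| 0.3 | 0.67 | 1.48 | 30% | 42% |
| 0.5 | 0.78 | 1.75 | 40% | 49% |
| 0.7 | 0.88 | 2.26 | 59% | 65% |
| 0.8 | 0.93 | 2.77 | 77% | 79% |
| 0.9 | 0.98 | 3.91 | 97% | 97% |

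**Break-even.** Setting the ratio to 1 gives rho = 60/31 - 1 = 0.935, or about 0.94. This needs equal SDs. If the post SD is k times the pre SD, the two variances are proportional to 1 + k^2 - 2k rho and k^2 (1 - rho^2) x 31/30. The change score is then more precise only within a band:

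| k | Change score better for rho from / to |
|---|---|
| 1.1 | 0.80 / 0.96 |
| 1.2 | 0.70 / 0.91 |
| 1.3 | 0.63 / 0.86 |

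Its best case is k x rho = 1, where a slope of 1 is exactly right and the ratio change/ANCOVA is 30/31 = 0.97, an advantage of about 3%.

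**The trigger.** With 20 per arm the baseline test fires at a gap of t(0.975, 38) x sqrt(2/20) = 2.024 x 0.316 = 0.64 SD or more. Below that, the change score over-corrects by (1 - rho) x gap. At a gap just under 0.64 SD this is 0.45 / 0.32 / 0.19 / 0.13 / 0.06 SD for rho 0.3 / 0.5 / 0.7 / 0.8 / 0.9. Type I error conditional on that gap is 17 / 13 / 10 / 8 / 7%. This is the worst case: at the median gap (0.21 SD) it is 2.9 to 4.7%.

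**The two-step rule.** In simulation its overall type I error is 4.1 to 4.9%. It recovers almost none of ANCOVA's gain: at N = 34 and rho = 0.5, with the effect set so that the change score has about 80% power, power is 79.9% for change score alone, 80.6% for the two-step rule and 88.8% for ANCOVA throughout.

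**The case against.** The best defence is that the mixed ANOVA is a legitimate analysis of a randomised comparison. It already uses the Day 1 value, it is unbiased over randomisations, and the two-step rule is if anything slightly conservative. All of that stands. A reader might infer that the planned analysis is biased or that the baseline trigger produces false positives overall; the figures do not support either. The 7 to 17% conditional error belongs to one extreme gap, not to a typical trial.

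It is also fair that the gain depends on a correlation the documents do not give, and that 0.94 is not a general threshold. Unequal SDs are plausible for pain, because entry requires participants "to complete the VAS for pain with a score less than 4/10 required", which limits the baseline spread but not the follow-up spread. In that case change scores may be slightly better at moderate to high rho. This weakens any claim that ANCOVA always wins. It does not remove the asymmetry under these assumptions: the possible loss is about 3% of variance, while with equal SDs the possible gain at rho = 0.3 is a third.

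The scope is uncertain too. The ANCOVA sentence may describe covariates used for other outcomes, so that only two outcomes were adjusted is the natural reading, not an established fact.

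Finally, one might infer that VAS, NDI and JPE rotation right were compared at follow-up with baseline ignored. The Mann-Whitney sentence names no time point and follows the baseline t-test sentence, so it may be a baseline comparison. The mixed-ANOVA sentence exempts no outcome.

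**Conclusion.** The point holds as a matter of efficiency and clear specification, not validity. On the natural reading, a baseline p-value decided which outcomes were analysed by ANCOVA, and the others received a change-score test. With 17 per arm and equal SDs, ANCOVA would cut variance by 33% at rho = 0.3, 22% at 0.5, 12% at 0.7, 7% at 0.8 and 2% at 0.9. For an assumed 0.6 SD effect the power gain runs from 12 percentage points to none.

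The size rests on an unknown rho, an assumed effect and, for the 0.94 break-even, equal SDs. It would be wrong to take rho of about 0.3 from the agreement with the sample size of 40: the SAP states neither the effect-size metric, the test nor the correlation, and other combinations give the same total. This is a change the sponsor should make, with medium confidence because the scope of the ANCOVA sentence is unclear.

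**What to change.** - For every intervention-versus-control outcome, fit ANCOVA with the follow-up value at a named visit as the response, and group and that outcome's own Day 1 value as the explanatory terms, whatever the baseline p-value.
- Specify the Day 1 value taken before the in-lab TENS session. Protocol section 8c has the intervention group measured again after that session on the same day.
- Keep baseline comparisons descriptive and remove them as a trigger.
- State which outcomes the present ANCOVA sentence covers, and with which covariates.
- Clarify two items so that the follow-up value is defined: the time point of the Mann-Whitney comparison, and how the SAP's two-week follow-up relates to the protocol's Day 8 and Day 30 visits.
- Label the change post hoc, since the protocol named only ANOVA and the baseline results had been seen, and report the SAP's mixed ANOVA beside it.

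The cost is SAP wording, one degree of freedom per model and an SPSS rerun, with no new data. At high rho there is little or no gain, and within the bands above a loss of at most about 3% of variance.

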4. STUDY INFORMATION

Location(s) of Research Activity: SAHP Neuroscience Research Laboratory- [name].

Expected Start/Stop Dates of Research: July 1, 2022-June 30, 2023.

Special Time Sensitivities: N/A

Type of Research: Experimental

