- 1) To measure the immediate and short-term effects of TENS on subclinical neck or upper quadrant pain with the VAS, anxiety with the State-Trait Anxiety Inventory for Adults™, disability with neck disability index (NDI), disability and cervical spine proprioception Noraxon 3D Inertial Motion Capture System in subjects 20-40 years of age.
- 2) To measure pain, anxiety, disability, and cervical spine proprioception in subjects with and without neck or upper quadrant pain.
- 3) To compare compliance of TENS home usage in groups with and without short message system (SMS), text message, reminders.

c. Procedures involved (Research Interventions)

There will be three groups as follows: twenty subjects with no pain in the normal group; forty subjects with chronic subclinical neck or upper quadrant pain will be randomized into two groups: twenty subjects in the control group, and twenty subjects in the intervention group. The intervention group will be further randomized into two groups: ten subjects will receive instructions for home use of TENS with daily SMS text message reminders and ten subjects will receive instructions for home use of TENS without SMS text message reminders. We will aim for an equal distribution of males and females in each group.

First session (Day 1): Before starting the procedures, participants complaining of pain that are greater than 4/10 in the VAS will be excluded from the study as this will be greater of what we consider to be subclinical pain based on literature review and if the pain has been present less than three months. In addition, if participants with pain less than 4/10 pain receiving clinical pain treatment, have taken pain medication

within six hours of first session, have acute pain or contraindications for electrical stimulation would be excluded from the study. Following completion of the signing procedures, all participants will be given brief explanations before administration of the questionnaires.

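### The immediate effect of TENS in Objective 1 has no comparator: only the TENS arm is remeasured and tested at 30 minutes

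*SAP*

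**What the plan says.** Protocol section 8b, item 1, states the aim: "To measure the immediate and short-term effects of TENS on subclinical neck or upper quadrant pain with the VAS", with anxiety, disability and cervical proprioception as the other outcomes.

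Under section 8c (first session, Day 1), all groups complete the VAS, STAI, NDI and joint position error (JPE) test once. Both TENS subgroups then have a 30-minute session in the lab and repeat all four. Controls get no procedure in the lab, no second Day 1 measurement is described for them, and they are next measured on Day 8. Section 9 lists assessments by visit and adds no control retest.

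The SAP has one analysis that names the 30-minute time point: "In the intervention group, we examined changes in outcome variables over time (pre versus post 30 minutes versus post 2 weeks"), by repeated measures ANOVA or Friedman's test. Post hoc testing follows a significant overall result: "Bonferroni's post hoc comparisons were conducted, or Wilcoxon signed rank test were used". The longitudinal comparison between arms is restricted to the later time: "Changes in outcome variables by group (intervention versus control) overtime (post 2 weeks versus pre) were assessed using 2x2 mixed factorial" ANOVA. Its reading rule is "If there was a significant interaction between group and time, the changes are significantly different between the two groups". Separate paired tests are run in each group "over time (post versus pre) were examined using paired t-test or Wilcoxon signed rank test", without saying which visit counts as post. Protocol section 11 says only that ANOVA will be used.

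**The concern.** The word *effects* in Objective 1 is causal, and the protocol justifies the study by the need for randomised trials of TENS. For the immediate part of that objective, randomisation is not used. The 30-minute result is a before-after change in one arm, whose participants have just repeated the same questionnaires and the same position-matching task, sat through a 30-minute session, and know they received an active device. Each of these can move the VAS, state anxiety or JPE without any action of the current.

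The control arm could have dealt with most of this. It is randomised and measured at baseline in the same session, but contributes no data at 30 minutes. A significant change filed under Objective 1 as worded would be read as an immediate effect of TENS, which this design cannot show.

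**Working it through.** **1. Which data exist at each time, and which test uses them**

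| Time | TENS arm | Control arm | Between-arm test over time in SAP |
|---|---|---|---|
| Day 1, baseline | measured | measured | reference value |
| Day 1, after 30 min | measured | not measured | none |
| SAP's 2 weeks | measured | measured | 2x2 mixed ANOVA |

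The SAP's rule for declaring a difference between groups uses the group-by-time interaction of that ANOVA, so it cannot reach the 30-minute row. The gap follows from the texts alone and needs no arithmetic.

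**2. How often a one-arm test is significant when TENS does nothing**

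The documents give no retest or practice shift, so this is an illustration.

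- Inputs from the documents: 20 in the TENS arm, or 20 × (1 − 0.15) = 17 after the stated 15% dropout; alpha 0.05.
- Assumed: a nonspecific shift of δ = 0, 0.2, 0.3 or 0.5 SD of the paired difference; normal data.
- Method: two-sided paired t, noncentral t with n − 1 df and noncentrality δ√n. For n = 20 and δ = 0.5 this is 0.5 × 4.472 = 2.236, against critical values of 2.625 at 0.05/3 (three pairwise times) and 2.093 at 0.05.

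| Assumed shift (SD) | 0.05/3: n=17 / n=20 | 0.05: n=17 / n=20 |
|---|---|---|
| 0 | 1.7% / 1.7% | 5% / 5% |
| 0.2 | 5.1% / 5.9% | 12.1% / 13.6% |
| 0.3 | 10.3% / 12.5% | 21.4% / 24.7% |
| 0.5 | 30.3% / 37.3% | 49.1% / 56.5% |

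The 0.05 column applies only if the SAP's separate paired tests include 30 minutes.

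The SAP runs post hoc tests only after a significant overall test. Simulating that gate (normal data, assumed correlation 0.5) gives about 5%, 9–12% and 29–36% for shifts of 0.2, 0.3 and 0.5 SD, about one point lower than the 0.05/3 column.

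A between-arm ANCOVA with the same shift in both arms (20,000 simulated trials, correlations 0.3 and 0.8, 17 or 20 per arm) rejects in 4.8–5.3%.

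**3. What a controlled 30-minute comparison could detect (80% power, two-sided 0.05)**

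The t-test on change uses 2n − 2 df and noncentrality d√(n/2). For ANCOVA on the baseline value with equal variances, the detectable difference is scaled by √((1+r)/2), with 2n − 3 df.

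| SD of change | 20 v 20 | 17 v 17 |
|---|---|---|
| t-test on change | 0.91 | 0.99 |
| ANCOVA, r = 0.3 | 0.73 | 0.80 |
| ANCOVA, r = 0.5 | 0.79 | 0.86 |
| ANCOVA, r = 0.8 | 0.86 | 0.94 |

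Example: 0.91 × √(1.3/2) = 0.91 × 0.806 = 0.73. Simulated ANCOVA power at these values is 0.78–0.79, the small loss coming from chance baseline imbalance.

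**The case against.** The SAP does not disguise what it does: the 30-minute test is labelled as within the intervention group, and the between-group rule is tied to the 2-week ANOVA. Neither document says the 30-minute result will be called a TENS effect. That is fair to the SAP. The mismatch lies with Objective 1, and a result reported under that objective takes on its wording.

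The data are probably already collected. The SAP is in the past tense and reports an observed result ("There was a significant difference in mean STAI_T and lateral flexion left between the intervention and control groups at baseline"), and the protocol's planned period was "Expected Start/Stop Dates of Research: July 1, 2022-June 30, 2023". If so, only reporting can change. This limits the remedy without removing the point.

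The rates rest on assumed shifts, and this stands. At 0.2 SD the Bonferroni rate is close to 5%. The rates are two-sided, and only a favourable shift could be mistaken for benefit. The unadjusted rates need a less natural reading of *post*, since those paired tests cover both groups and controls have no 30-minute value. Skewed outcomes would go to Friedman and Wilcoxon; a simulation of that route on normal data, with Wilcoxon at 0.05 after a significant Friedman test, gave about 5–6%, 9–13% and 30–39%, close to the Bonferroni figures.

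A control retest would not remove expectation, because there is no sham, and would detect only large differences. Both are true and should be stated with the fix.

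**Conclusion.** The concern holds. As planned, the immediate part of Objective 1 has no comparator, and no significance level applied to a one-arm change turns it into an effect of TENS. This conclusion rests on the Day 1 procedures and the SAP's list of tests, not on the illustration.

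The practical harm is uncertain: close to nominal if the nonspecific shift is about 0.2 SD, and roughly one false signal in three at 0.5 SD with Bonferroni adjustment. It should be corrected because the correction is cheap and changes what the trial may claim.

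The 2-week comparison is outside this point. Separately, the protocol schedules Day 8 and Day 30 rather than 2 weeks, and the two documents need to be reconciled.

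**What to change.** **If data collection is over.** Report the 30-minute result as an uncontrolled within-group change, with estimate and confidence interval, and do not present it as an immediate effect of TENS. Align Objective 1 with that wording, and state in the SAP which visit *post* means in the paired tests. This costs wording only.

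**If Day 1 visits are still open.** Have controls wait 30 minutes and repeat the VAS, state anxiety and JPE, then compare arms by ANCOVA on the baseline value. The NDI could be added so that the batteries match, but its sections on sleep, work, driving and recreation have little scope to change in half an hour. State in the plan that this removes retest, practice and time effects shared by both arms but not expectation, and give the detectable differences (0.91 SD of change for a t-test, about 0.73–0.86 for ANCOVA with 20 per arm).

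The cost is a longer first visit for 20 controls already in the lab, with the same staff and equipment. Battery length is not given. Assuming 10–20 minutes, each control adds 40–50 minutes: 20 × 40 = 800 to 20 × 50 = 1,000 minutes, about 13–17 lab hours in total.
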